10.1. Laboratory Samples

Blood, urine, and CSF samples will be collected to determine whether patients meet inclusion/exclusion criteria and to monitor patient health. Routine clinical laboratory tests will be analyzed by a central laboratory selected by Lilly or local laboratory (screening, coagulation and CSF protein, glucose, and cell counts).

Investigators must document their review of each laboratory safety report.

Laboratory/analyte results that could unblind the study will not be reported to investigative sites or other blinded personnel until the study has been unblinded.

Samples collected for specified laboratory tests will be destroyed within 60 days of receipt of confirmed test results. Tests are run and confirmed promptly whenever scientifically appropriate. When scientific circumstances warrant, however, it is acceptable to retain samples to batch the tests run, or to retain the samples until the end of the study to confirm that the results are valid. Certain samples may be retained for a longer period, if necessary, to comply with applicable laws, regulations, or laboratory certification standards.

10.2. Samples for Pharmacokinetic and Pharmacodynamic Evaluations

10.2.1. Pharmacokinetic Samples

At the visits and times specified in the Study Schedule, 1 venous blood sample of approximately 4 mL will be collected for each PK assessment ([Attachment 1](#)). These blood samples will be used to determine the serum concentrations of LY3002813. The actual date and time (24-hour clock time) of each sampling will be recorded. On the day of dosing, every attempt should be made to collect samples at the specified time; however, failure to do so will not constitute a protocol violation.

A maximum of 3 blood samples per patient may be drawn at additional time points during the study, if warranted and agreed upon between both the investigator and sponsor. Instructions for the collection and handling of blood samples will be provided by the sponsor.

On the dosing day, PK serum samples will be collected from the arm that did not receive the infusion of study drug.

Time points for PK may be modified based on interim PK results.

10.2.2. Cerebrospinal Fluid Samples

For patients undergoing LP, a lumbar x-ray or fluoroscopy may be conducted at screening to perform the procedure or rule out potential contraindication to a LP, such as significant osteoarthritic disease and bone overgrowth. If an x-ray or fluoroscopy was done within 12 months of screening, this may be used.

A qualified physician (eg, anesthesiologist or neurologist) will perform the LP under local anesthesia. At each LP, a maximum of 15 mL (including up to 5 mL for local laboratory testing) of CSF will be collected. The first 5 mL of CSF will be collected and sent to a local laboratory for testing of white blood cell count, red blood cell count (where possible), total protein, and glucose. In addition, each CSF sample will be visually inspected for evidence of blood contamination. The results of the visual inspection and local laboratory CSF analyses are to be documented on the electronic CRF (eCRF). Grossly evident blood by visual inspection will be reported as positive and documented in the CRF. The remaining CSF will be collected to measure concentrations of A β ₁₋₄₀, A β ₁₋₄₂, total tau, and phospho-tau measurements, as well as LY3002813 (see below) in patients who are randomly assigned to receive LY3002813. All other remaining CSF will be stored for exploratory work (Section 10.2).

Patients will be carefully monitored for post-LP headaches. The investigator may use hydration, analgesics, and blood patch to treat the headache, as clinically indicated.

Any sample that shows visual or laboratory evidence of blood contamination may be excluded from the PK and statistical analyses if the level of contamination is estimated to be sufficient to produce misleading results.

10.2.3. Bioanalysis

Samples will be analyzed at a laboratory approved by the sponsor and stored at a facility designated by the sponsor.

Serum and CSF concentrations of LY3002813 will be determined using a validated enzyme-linked immunosorbent assay method. It is not intended that samples collected from placebo-treated patients will be analyzed. Samples will be analyzed at a laboratory approved by the sponsor and stored within the United States.

Bioanalytical samples collected to measure investigational product concentrations will be retained for a maximum of 2 years following last patient visit for the study. During this time, samples remaining after the bioanalyses may be used for exploratory analyses such as metabolism and/or protein binding work.

10.2.4. Plasma Samples

Ethylene diamine tetraacetic acid (EDTA) plasma from a 6 mL collection tube will be analyzed for A β species, which includes A β ₁₋₄₀ and A β ₁₋₄₂. Other fragments of amyloid precursor protein processing or A β plaque species may be analyzed.

10.2.5. Pharmacodynamic Evaluations

See Section [10.5.2](#) for further details.

10.3. Samples for Biomarker Research

There is growing evidence that genetic variation may impact a patient's response to therapy. Variable response to therapy may be due to genetic determinants that impact drug absorption, distribution, metabolism, and excretion, the mechanism of action of the drug, the disease etiology and/or the molecular subtype of the disease being treated. Therefore, where local regulations and ERBs allow, a 1-time blood sample will be collected for pharmacogenetic analysis ([Attachment 1](#)).

Collection of samples for other biomarker research is also part of this study. Blood and CSF samples will be collected as specified in the Study Schedule.

The CSF, plasma, and serum stored samples may be used for research to develop methods, assays, prognostics, and/or companion diagnostics related to AD and or other neuropathological conditions.

Blood samples for biomarker research are required and will be collected from all patients in this study as specified in the Study Schedule ([Attachment 1](#)).

Samples will be tested for the apolipoprotein E (APOE) genotype ($\epsilon 2$, $\epsilon 3$, $\epsilon 4$) and translocase of outer mitochondrial membrane 40 (TOMM40) poly-T polymorphism to determine whether these genetic variants are associated with response to LY3002813. APOE genotype, which is in linkage disequilibrium with TOMM40, has been demonstrated even in small sample sizes to be associated with vasogenic edema complications; thus, the analysis of these genes is planned. In addition, where local regulations allow, the sample will be stored and analysis may be performed on other genetic variants thought to play a role in response to LY3002813, response to antidementia concomitant therapy, and/or molecular subtypes of AD to test their association with observed clinical outcomes when taking the study drug. While it is unlikely that signals from small trials can be suggested by genetic variance, samples may be saved for analysis particularly for retrospective review if future studies detect associations or other researchers report significant findings. At the current time, possible target genes include, but are not limited to, Fc γ RII, Fc γ RIII, CLU, CR1, PICALM, MAPT, BIN1, PSEN1, and PSEN2.

CSF samples remaining after local laboratory studies, LY3002813 PK, amyloid species, and tau species testing are complete may be retained as stored samples for a maximum of 15 years for use as described above. The following list of potential exploratory biomarkers does not preclude future molecules of interest but may include VILIP-1, YKL40, β -amyloid fragments, interleukins, tumor necrosis factor alpha, and inflammatory cytokines.

EDTA plasma from a 6-mL collection tube and serum from a 6-mL collection tube will each be aliquoted into 5 respective 0.5-mL aliquot volumes for a total of 10 aliquots (5 EDTA plasma and 5 serum). These samples will be stored for biomarker research and development. The following list of potential exploratory biomarkers does not preclude future molecules of interest

but may include VILIP-1, YKL40, β -amyloid fragments, interleukins, tumor necrosis factor alpha, and inflammatory cytokines.

ABI TempusTM tubes (3 mL blood) for ribonucleic acid extraction and exploratory gene expression will be collected/processed and stored for future analysis.

In the event of an unexpected AE or the observation of unusual response, the pharmacogenetic samples may be genotyped and analysis may be performed to evaluate a genetic association with response to LY3002813. These investigations may be limited to a focused candidate gene study or, if appropriate, genome wide analysis may be performed to identify regions of the genome associated with the variability observed in drug response. The pharmacogenetic samples will only be used for investigations related to disease and drug or class of drugs under study in the context of this clinical program. They will not be used for broad exploratory unspecified disease or population genetic analysis.

Other samples may be used for research to develop methods, assays, prognostics and/or companion diagnostics related to disease process, pathways associated with disease state, and/or mechanism of action of the investigational product(s).

The samples will be coded with the patient number and stored for up to a maximum of 15 years after the last patient visit for the study at a facility selected by the sponsor. The samples and any data generated from them can only be linked back to the patient by investigator site personnel. The duration allows the sponsor to respond to regulatory requests related to the investigational product.

An 11-mL blood sample for pharmacogenetic evaluation is a required part of this study, unless country-specific laws and regulations prohibit this type of testing. A 3-mL tube will be used for APOE genotypes and TOMM40 polymorphisms, a 4-mL tube will be used for DNA extraction, and a 4-mL tube of whole blood will be stored. These samples will be used to test for genetic variants that may influence response to treatment.

Samples will be destroyed according to a process consistent with local regulation.

10.4. Samples for Immunogenicity Research

Blood samples for immunogenicity testing will be collected to determine antibody production against the investigational product. Additional samples may be collected if there is a possibility that an AE is immunologically mediated. Immunogenicity will be assessed by a validated assay designed to detect ADAs in the presence of the investigational product. Antibodies may be further characterized and/or evaluated for their ability to neutralize the activity of the investigational product.

Samples may be stored for a maximum of 15 years following last patient visit for the trial at a facility selected by the sponsor to enable further analysis of immune responses to the investigational product. The duration allows the sponsor to respond to regulatory requests related to the investigational product.

10.4.1. Additional Immunogenicity and Safety Visits for all Cohorts

If the immunogenicity titer at the last scheduled assessment or discontinuation visit is positive, then additional safety assessments (concomitant medications, AEs, laboratory values, vital signs, ECGs) and samples for immunogenicity and PK should be taken every 12 weeks until the titer returns to baseline (comes within a single 2-fold dilution of the baseline titer) or up to 48 weeks after the last dose of LY3002813 if the antibody titer has not returned to baseline within 48 weeks after the last dose. In the case of a patient whose result is positive at baseline with a 1:10 titer and then subsequently develops a treatment-emergent ADA response that increases to much higher titers, the antibody titer would need to decline to a titer of 1:20 or less to be considered a “return to baseline.” In contrast, if the patient’s result is “not detected” at baseline (in an assay with a 1:10 minimal required dilution), the titer would need to decline to either “detected” with a 1:10 titer or a result of “not detected” to be considered a “return to baseline.”

10.5. Exploratory Evaluations

10.5.1. Cognitive and Functional Scales

The test of cognitive function, ADAS-cog, NTB, MMSE, Clinical Dementia Rating - Sum of Boxes (CDR-SB), Alzheimer’s Disease Cooperative Study-Mild Cognitive Impairment-Activities of Daily Living (ADCS-MCI-ADL) scale, and FCSRT-IR will be performed during the study at the times specified in the Study Schedule ([Attachment 1](#)). These tests are performed as a safety and exploratory measure to document any substantial change associated with treatment, as it is not anticipated that these tests should have significant changes associated with LY3002813 in this small patient population and short time window. Cognitive and functional tests that are performed on the same day should be done in a specific order. Screening tests should be completed in this order: 1) MMSE, 2) FCSRT-IR, and 3) CDR. The other scales, if done on the same day, should be performed in this order: 1) NTB, 2) ADCS-MCI-ADL, and 3) ADAS-cog. The study partner (or 1 of the study partners if there are 2) should be present or available by telephone for the assessment of CDR and ADCS-MCI-ADL (this should be the primary study partner for ADCS-MCI-ADL).

10.5.1.1. Alzheimer’s Disease Assessment Scale-Cognitive Subscale

The ADAS was designed as a rating scale for the severity of the dysfunction in the cognitive and noncognitive behavior characteristic of persons with AD (Rosen et al. 1984). The cognitive subscale of the ADAS (ADAS-cog[11]) consists of 11 items assessing areas of function most typically impaired in AD: orientation, verbal memory, language, and praxis. The scale ranges from 0 to 70, with higher scores indicating greater disease severity. An extended ADAS-cog (the ADAS-cog[14]) which includes measurements of delayed free recall, digit cancellation, and maze completion will be used in this study (Mohs et al. 1997). A conversion code of 0 to 10 for delayed free recall and 0 to 5 for both digit cancellation and maze completion provide a total ADAS-cog[14] score that ranges from 0 to 90.

10.5.1.2. Neuropsychological Test Battery

The NTB is a cognitive tool for clinical trials in the field of AD. The NTB is a collection of several written and oral tests that examines verbal and nonverbal brain functions. The NTB shows linear annual cognitive changes across a wide range of MMSE scores as compared to the ADAS-cog and is more sensitive than the ADAS-cog among patients with mild impairment (Harrison 2007).

10.5.1.3. Mini-Mental Scale Examination

The MMSE is one of the most widely used screening instruments for cognitive impairment and provides a total score ranging from 0 to 30, with lower scores indicative of greater cognitive impairment (Folstein et al. 1975).

10.5.1.4. Clinical Dementia Rating

The CDR is a clinical staging instrument for Dementia (Morris 1993). It characterizes 6 domains of cognitive and functional performance: memory, orientation, judgment and problem solving, community affairs, home and hobbies, and personal care. The necessary information to make each rating is obtained through a semistructured interview of the patient and a reliable informant or collateral source (eg, a family member). The CDR table provides descriptive anchors that guide the clinician in making appropriate ratings based on interview data and clinical judgment. In addition to ratings on a 5-point scale for each domain (except for personal care, which is rated on a 4-point scale), an overall CDR score is derived by standard algorithm. This score is useful for globally staging the level of impairment: 0 indicates no impairment; 0.5, 1, 2, and 3 indicate very mild, mild, moderate, and severe dementia, respectively.

10.5.1.5. Clinical Dementia Rating—Sum of Boxes

The CDR-SB is considered a more detailed quantitative general index than the global score and has reasonable accuracy to discriminate between patients with very early AD and those with MCI.

10.5.1.6. Alzheimer's Disease Cooperative Study/Activities of Daily Living Scale

The ADCS-MCI-ADL is a 24-item questionnaire that attempts to detect milder functional impairments and represent a modification of the original activities of daily living scale (Galasko et al. 1997).

10.5.1.7. Free and Cued Selective Reminding Test with Immediate Recall

The FCSRT-IR is a 16-item instrument version of controlled learning (Grober and Buschke 1987). FCSRT-IR performance as an indicator of early AD comes from correlations with abnormalities in structural and functional imaging and with neurofibrillary lesions in parahippocampal regions that are the earliest targets of AD pathology.

10.5.2. Imaging

A total of two 18F-AV-1451 PET scans will be performed, approximately 72 weeks apart, except for Cohort 3 where scans will be approximately 24 weeks apart. 18F-AV-1451 PET scan should be performed at least 24 hours apart from the florbetapir scan (for further details on florbetapir imaging see Section 9). The change in grey matter SUV_r will be compared to total dose

exposure. Additional approaches for tau PET quantitation may be applied based on emerging data.

MRI changes in brain volume over the course of the study will be explored. Over an approximate span of 72 weeks, except for Cohort 3, which will be 24 weeks, screening MRI and up to 8 post-baseline MRIs will be performed, mostly for safety monitoring (i.e., occurring 4 weeks after the first dose, every 12 weeks starting from the first dose, and up to 12 weeks after the last dose). However, additional MRI scans are included for exploratory evaluation of brain structural changes (including, but not limited to, whole brain, ventricle, and hippocampal volumes), white matter and tissue microstructure changes, and functional connectivity in brain networks at baseline, 24 weeks, 48 weeks, and 72 weeks as applicable.

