Part C (Cohorts 6 and 7): 19 doses of LY3002813 or placebo administered Q4W for 72 weeks followed by 12-weeks follow-up

Criteria for Evaluation:

Safety: Safety parameters that will be assessed include AEs, concomitant medications, cognitive function, physical and neurological examinations, vital signs, electrocardiogram, safety laboratory values, and MRI scans.

Bioanalytical: Serum and CSF samples will be used to determine concentrations of LY3002813. Serum and CSF concentrations of LY3002813 will be determined by validated enzyme-linked immunosorbent assay.

Pharmacogenomics: A blood sample will be used to test for genetic variants that may influence response to treatment.

Pharmacokinetic/Pharmacodynamic: Blood and CSF samples will be used to determine the concentrations of LY3002813. Cortical standardized uptake value ratio (SUVr) from florbetapir and 18F-AV-1451 positron emission tomography scans will be analyzed to estimate mean change. The CSF results from the lumbar punctures taken pre- and postinfusion will be analyzed to estimate the mean change from preinfusion. The dependent variables are $\text{A}\beta_{1-40}$, $\text{A}\beta_{1-42}$, total tau, and phospho-tau.

Statistical Evaluation Methods:

Up to approximately 150 patients may be enrolled to ensure that a minimum of approximately 72 patients complete the study. The sample size is customary for studies evaluating safety, PK, and/or PD parameters; at the conclusion of the trial, confidence intervals for PK, PD, and cognition endpoints may be computed in order to evaluate the precision of the estimates where appropriate. In addition, based on prior Lilly clinical trials, 6 patients randomized to each LY3002813 dose and placebo provide over 90% power to detect at least a 17% mean florbetapir SUVr reduction of a dose compared to placebo without multiple comparison adjustment.

Statistical: PK/PD analyses will be conducted on the full analysis set. This set includes all data from all randomized patients receiving at least 1 dose of the investigational product according to the treatment the patients actually received. Safety analyses will be conducted for all enrolled patients, whether or not they complete all protocol requirements. A model-based approach of analysis will be used. Summary statistics, data tabulations, and data graphs by ethnicity (Japanese and non-Japanese) will be provided as appropriate.

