7.1.5. Part C: Chronic, 72-Week Q4W Multiple Dose Cohorts (Cohorts 6 and 7)

Safety, PK, and PD will be assessed in Cohorts 6 and 7 during and after multiple doses of LY3002813 or placebo have been administered Q4W for up to 72 weeks, or when the LY3002813-induced reduction in amyloid measured by florbetapir reaches the maximum reduction (defined as SUVr <1.1 for 2 consecutive scans) (Joshi et al. 2015). The planned doses are 10 and 20 mg/kg IV with 12 patients (9 LY3002813; 3 placebo) planned to be enrolled in each cohort. Cohort 6 (10 mg/kg IV Q4W) and Cohort 7 (20 mg/kg IV Q4W) may proceed, in parallel with Cohorts 4 and 5, respectively. In addition, Cohort 7 will only be initiated after confirmation that at least 2 patients have received at least 2 doses each of LY3002813 safely in Cohort 6. The maximum dose of 20 mg/kg will not be exceeded. If a patient is deemed to be amyloid negative by florbetapir PET before completion of 18 months' dosing (SUVr <1.1 for 2 consecutive scans), the patient will receive placebo infusion for all subsequent visits and continue the Part C visit schedule, including assessment of sustained amyloid reduction at the scheduled PET scan assessments. Safety, PK, and PD will be assessed for all patients at regular intervals for approximately 12 weeks after completion of 72 weeks of dosing with LY3002813 ([Attachment 1](#)).

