- r Predose and end of infusion samples should be collected. The “predose” collection indicates that the sample should be taken up to 30 minutes before the beginning of the infusion. The “end of infusion” collection indicates that the sample should be taken as close to the completion of the infusion as possible. Postdose samples should be collected from a different arm than was used to administer study drug.

- s If the immunogenicity titer at the last scheduled assessment or discontinuation visit is positive, then additional safety assessments (concomitant medications, AEs, safety laboratory values, ECGs, vital signs) and samples for immunogenicity and PK should be taken every 12 weeks until the titer returns to baseline (comes within a single 2-fold dilution of the baseline titer), or up to 48 weeks after the last dose of LY3002813 if the antibody titer has not returned to baseline within 48 weeks after the last dose. In the case of a patient whose result is positive at baseline with a 1:10 titer and subsequently develops a treatment-emergent ADA response that increases to much higher titers, the antibody titer would need to decline to a titer of 1:20 or less to be considered a “return to baseline.” In contrast, if the patient’s result is “not detected” at baseline (in an assay with a 1:10 minimal required dilution), the titer would need to decline to either “detected” with a 1:10 titer or a result of “not detected” to be considered a “return to baseline.”
- t Stored serum samples for possible immune safety laboratory testing (including but not limited to β tryptase, total Immunoglobulin E, and immune complex testing) will be collected. In the event of a moderate or severe infusion reaction event, additional unscheduled samples should be collected approximately 60-120 minutes and 4-6 weeks after moderate or severe infusion reactions. Failure to collect these samples will not qualify as a protocol violation. Unscheduled samples may also be collected as needed.
- u Performed predose and end of infusion and 2 hours after the end of infusion on dosing days.
- v Performed predose and end of infusion.
- w If a patient is deemed to be amyloid negative by florbetapir PET before completion of 18 months’ dosing (SUVr <1.1 for 2 consecutive scans), the patient will receive placebo infusion for all subsequent visits, and continue the Part C visit schedule.

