#### **4.2.5.3. Pharmacodynamic Cerebrospinal Fluid Estimation**

The CSF results from the LPs taken pre- and postdose will be analyzed to estimate the mean change and percent change from predose. The dependent variables are A $\beta$ 1-40, A $\beta$ 1-42, , total tau, and phospho-tau concentrations. Using an ANCOVA model, IV dosing regimen will be a fixed effect with the baseline concentration as a covariate in the model. These analyses are considered exploratory in order to estimate mean change and the variance of the change following IV single, multiple and chronic doses of LY3002813. A logarithmic transformation may be used to ensure valid statistical estimation properties.

In addition to these analyses, correlation analyses between changes in CSF biomarkers (A $\beta$ 1-40, A $\beta$ 1-42, total tau, phospho-tau), or imaging endpoints (MRI measures, or SUVr from florbetapir scans) with posthoc serum AUC estimates derived from the PK model (or an alternative measure of exposure if deemed appropriate) may be completed. For SUVr, this will be conducted for the individual regions (if collected) and the total SUVr. Additionally, CSF and/or serum LY3002813 exposures may be related to CSF biomarkers, as appropriate.

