### **4.2.6. Pharmacokinetic/Pharmacodynamic Analyses**

Exploratory correlational analyzes may be conducted to describe the relationship between exposure and changes in the florbetapir SUVr; MRI of whole brain, ventricle, and hippocampus volumes; CSF concentrations of abeta, tau and ptau; maximum ADA levels; and number AEs related to infusion reactions. It is intended that these analyses will be descriptive graphs in nature as a function of LY3002813 dose, exposure, and/or time from study entry; however, the relationship may also be described using a modeling approach, if appropriate.

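### In Part C the total dose received depends partly on the amyloid response, so exploratory comparisons of imaging change with total dose or cumulative AUC can mislead; assigned regimen or pre-switch exposure should be used

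*Protocol*

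**What the plan says.** - Protocol 10.5.2 (Imaging), in the paragraph on 18F-AV-1451 scans: "The change in grey matter SUV_r will be compared to total dose" exposure. This is stated as planned, not optional. No method is named.
- SAP 4.2.5.3 covers correlations of CSF biomarkers, MRI measures or florbetapir SUVr "with posthoc serum AUC estimates derived from the PK model (or an alternative measure of exposure if deemed appropriate) may be completed". Tau PET is not in that list, and the period over which AUC is taken is not given.
- SAP 4.2.6 allows exploratory work on the "relationship between exposure and changes in the florbetapir SUVr", also with no window. Protocol 11.2.5.1 and 11.2.6 allow similar analyses.
- Protocol 7.1.5 sets Part C dosing to run up to 72 weeks or until amyloid "reaches the maximum reduction (defined as SUVr <1.1 for 2 consecutive scans"). From that point "the patient will receive placebo infusion for all subsequent visits and continue the Part C visit schedule". Footnote w of Attachment 1 repeats the rule.
- SAP 4.2.5.1 gives a different tau analysis: an ANCOVA with IV dose group as the factor and baseline SUVr as covariate.

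Neither document says how a patient switched to placebo enters an exposure analysis. The analysis-set rule (Protocol 11.2.1, SAP 4.2.1) groups patients by treatment actually received, which does not settle it.

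**The concern.** An exposure-response comparison is informative when exposure is set independently of the outcome. In Part C it is not. A patient who clears amyloid quickly stops receiving drug early and ends with a low total dose; a slow clearer receives all planned infusions. Total dose at Week 72 is partly a readout of amyloid response, so zero correlation is no longer what a lack of exposure effect implies. A real effect of exposure on clearing also works against itself, because better exposure leads to fewer doses.

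The first exploratory objective is the relation among dosing regimens, PK and florbetapir PD, and Protocol 5.2 links the results to dosing selection. A flattened or wrong-signed exposure relation would be unhelpful there. The dosing rule itself is not in question, only the choice of explanatory variable.

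**Working it through.** **Dose count.** The plan's figure is "19 doses of LY3002813 or placebo administered Q4W for 72 weeks". Infusions = 72/4 + 1 = 19, which matches. Part B as a check: 24/2 + 1 = 13, also a match.

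**Active infusions after a switch.** Florbetapir scans fall at Weeks 12, 24, 36, 48 and 72 (Protocol 7.1). Active infusions = (week of second consecutive scan below 1.1)/4 + 1, with placebo from the next visit (one more active dose if the read is late).

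| Second scan below 1.1 | Active infusions | Cohort 6 (10 mg/kg) | Cohort 7 (20 mg/kg) |
|---|---|---|---|
| Week 24 | 24/4 + 1 = 7 | 70 mg/kg | 140 mg/kg |
| Week 36 | 36/4 + 1 = 10 | 100 | 200 |
| Week 48 | 48/4 + 1 = 13 | 130 | 260 |
| Week 72 or never | 19 | 190 | 380 |

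A fast clearer in Cohort 7 (140) can have received less drug than a slow clearer in Cohort 6 (190), so the dose order can reverse. This needs no modelling assumption.

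**Patients affected.** "The planned doses are 10 and 20 mg/kg IV with 12 patients (9 LY3002813; 3 placebo) planned to be enrolled in each cohort" gives 9 + 9 = 18 active patients in Part C, out of 6×3 + 9×4 = 54 planned actives.

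**Effect on inference, by simulation.** The documents give no SUVr spread, clearing rate or amyloid-tau correlation, so all of these are assumptions. Model: SUVr(t) = floor + (baseline − floor)·exp(−k·t) + scan noise (SD 0.03), with k varying log-normally between patients and the switch rule applied at the scheduled scans. Tau change = −ρ·z + √(1 − ρ²)·e, where z is the patient's standardised log clearing rate and e is independent noise. Test: Pearson correlation, two-sided 5%.

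- Set 1: baseline 1.58 (SD 0.2), floor 1.0, median k 0.03-0.06 per week, log-SD 0.3-0.5, drug clearance CV 30%; 14-71% of patients switch.
- Set 2: baseline mean 1.4-1.7 (SD 0.15), floor 0.95, median k 0.03 per week, log-SD 0.6, 20 mg/kg clearing 1 to 2 times as fast as 10 mg/kg; 26-69% switch.

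| Quantity | Total dose | Alternative |
|---|---|---|
| False rejection for tau, Part C cohorts pooled, ρ = 0.5 | 5-18% (set 1); 11-24% (set 2) | 4-6% (Week 24 exposure, set 1); 4.5-5.8% (assigned dose, set 2) |
| Same, ρ = 0 | 4-6% | 4-6% |
| False rejection for tau, all 54 actives | 5-9% (set 1, ρ = 0.5); 6-11% (set 2, ρ = 0.3-0.7) | 4-6% (assigned dose, set 2) |
| Power for tau in the right direction, clearing rate proportional to exposure, Part C (set 1) | 1-7% (cumulative AUC 4-26%) | 28-45% (Week 24 exposure) |
| Power for amyloid, 20 mg/kg clears twice as fast, Part C (set 2) | 2-10% | 14-31% (assigned dose) |
| Same, 1.5 times as fast | 1-6% | 8-16% (assigned dose) |

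A stronger amyloid-tau link gives more. At ρ = 0.7 in set 2 (baseline 1.55), Part C false rejection is 22-36%.

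**Direction.** With no dose effect on tau and ρ = 0.5, the set 2 correlation of total dose with tau change is +0.17 to +0.31: more drug appears to go with worse tau. For amyloid the sign depends on assumptions. Set 2 with no dose effect gives +0.02 to +0.15 (more drug, less removal). Set 1, with a wider baseline spread, gives the opposite within a cohort, because patients with low baseline SUVr cross 1.1 early with a small change and few doses.

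**The case against.** The strongest case against has four parts.

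1. *The likely analysis pools all cohorts.* Protocol 10.5.2 is not limited to Part C, and no text plans a correlation within one Part C cohort. A reader might infer very high error rates, because single-cohort correlations in set 1 reject falsely in 10-34% of trials for tau and 9-41% for amyloid. Those rates belong to an analysis the documents do not specify. Over all 54 actives the tau rate is about 5-11%. This stands, and it limits the size of the false-effect claim.

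2. *The SAP already has a sound tau model.* Protocol 11.2.1 leaves the detail of analyses to the SAP, and the SAP 4.2.5.1 ANCOVA uses dose group. This stands if dose group means assigned regimen. It leaves the two documents describing different tau analyses.

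3. *The exposure work is optional and mostly graphical, and the AUC window is open.* True of SAP 4.2.5.3 and 4.2.6. A reader might infer that AUC will be cumulated to Week 72; the documents do not say so, and SAP 4.2.5.3 already allows another exposure measure. But nothing steers the analyst away from cumulative AUC, and the tau comparison with total dose is stated as planned.

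4. *A Week 24 cut-off everywhere would do harm.* Pooled across Parts, a 72-week Part C patient would be credited with at most 7 infusions against 13 for a Part B patient at the same mg/kg. This stands, and the fix allows for it.

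**Conclusion.** The point holds for exploratory exposure-response analyses that use Part C total dose, or AUC accumulated past Week 24. That these quantities depend on amyloid response follows directly from the protocol. Within Part C, the better supported consequence is loss or reversal of a true exposure relation: power of 1-7% with total dose against 28-45% with Week 24 exposure for tau in set 1. False rejection for tau is roughly 5-24% with the two Part C cohorts pooled at an assumed amyloid-tau correlation of 0.5. It returns to nominal if that correlation is zero, and is about 5-11% over all cohorts. The share of patients who switch is unknown.

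A reader might infer that the primary amyloid result is compromised. The documents do not support that: the primary MMRM compares dose groups, as does the SAP tau ANCOVA, and both are unaffected if dose group means assigned regimen. The change is worth making because the wording as it stands leads to a biased comparison and is easily corrected.

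**What to change.** Analysis wording only:

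- **Protocol 10.5.2:** replace total dose exposure with the assigned dose regimen, so that it matches the SAP 4.2.5.1 tau ANCOVA. State there that a Part C patient switched to placebo stays in the assigned dose group.
- **SAP 4.2.5.3 and 4.2.6, analyses within Part C:** use exposure not altered by the switch, either AUC from first dose to the Week 24 visit or average concentration per active dosing interval. The second still averages over a number of intervals that depends on the switch, so it relies on concentrations being reasonably stable between intervals.
- **SAP 4.2.5.3 and 4.2.6, analyses pooled across Parts:** use assigned regimen or average concentration per active interval, not a Week 24 cut-off.
- **Any display against cumulative Part C dose or AUC:** label it descriptive, with no test and no causal reading.

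Cost: no new data, visits or dosing changes. If Week 24 AUC is chosen, individual exposure after Week 24 is not used as an explanatory variable within Part C.
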